 5. Delirium
 6. Septic Shock
2. Postoperative ICU admission (yes/no)
3. Prolonged Postoperative Length of Stay (LOS) (greater than vs. less than or equal to CIHI Expected Length of Stay (ELOS) as assigned by the Case Mix Grouping) [note that the LOS includes the day of surgery]
4. Hospital readmission within 30 days (yes/no)
5. Intraoperative mortality (yes/no)
6. Days alive and out of hospital at 30 days postoperatively (28)

III. Other predictors included into model

The following potential perioperative predictors will be evaluated as covariates during model building. Statistically significant predictors will be retained in the model.

Table 2. Other predictors

Preoperative	
 1. Demographics: age on date of surgery, sex, obesity (body mass index>30) 2. Indicators of preoperative comorbidities: since no comorbidity score has perfect performance, a variety of models will be evaluated and the most significant predictive score will be retained in the model. 
 • American Society of Anesthesiologist class • RCRI score(29), and specific components via ICD codes (history of ischemic heart disease, congestive heart failure, cerebrovascular disease, diabetes, chronic kidney disease, and CCI and Case Mix Group codes of suprainguinal vascular, intraperitoneal, or intrathoracic surgery) using previously published methods (30)(31) • Elixhauser comorbidity index (32) and Charlson Comorbidity Index (33): calculated using diagnoses from the previous three years according to standard algorithm by HDNS. Reported as both total score and individual categories • Hospital Frailty Risk Score (34): based on ICD codes • Preoperative blood pressure: ICD diagnosis of hypertension and by measured blood pressure • Preoperative heart rate: Innovian and HSM • Chronic Obstructive Lung Disease (ICD code): since it may affect the interpretation of results of SpO₂ and EtCO₂ 3. Indicators of surgical complexity 
 • CIHI DAD Case Mix Group (CMG) class (also contains categories that include medical complexity) • Main Surgical Service • Procedural Index for Mortality Risk (PIMR) (35): according to CCI • Procedure: CCI codes • Preoperative ICU admission • Emergency surgery: as determined by DAD Method of Entry = emergency department or transferred from another institution)

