CIHI DAD	PATIENT_ID: encrypted health card number For HDNS internal use	Patient	Jan 1, 2013 to Dec 1, 2017	HDNS data linkage with Innovian-HSM. The dataset given to us will not contain Patient_ID, but rather a Study ID.
Vital Statistics	PATIENT_ID: encrypted health card number For HDNS internal use	Patient	Jan 1, 2013 to Dec 1, 2017	HDNS data linkage with Vital Statistics. The dataset given to us will not contain Patient_ID, but rather a Study ID.
CIHI DAD	PDATE[1-n]: procedure date	Patient	Jan 1, 2013 to Dec 1, 2017	HDNS data linkage with Innovian surgery date, to ensure that only the admission corresponding to the surgery admission of interest (first surgery admission with LOS>1) is included.

				
The PDATE matching the date of procedure (+/- 1 day) from Innovian will be used. The corresponding number (e.g. PDATE1) will be used for all procedure-related codes (e.g. PCODE1, PDSERV1).
 
Note that except for preoperative comorbidity data, where we would need data for 3 years prior to PDATE, for all other variables we only need data within 30 days after PDATE.

CIHI DAD	
LOS: Length of Stay (after surgery)
 
Derived by HDNS: discharge date minus PDATE + 1 (includes day of surgery)
	Patient	
Jan 1, 2013 to Dec 1, 2018 (to account for prolonged LOS postop from the end of inclusion date)
	
Part of inclusion criteria: if a patient had multiple surgeries, the first surgery with a LOS >1 (i.e. at least overnight stay). To calculate ratio of LOS to Expected Length of Stay (ELOS) as secondary outcome. We have chosen to standardize LOS to only include duration of stay after surgery, since there are many factors that may prolong a patient's stay prior to surgery.

Additional Demographic Information				
CIHI DAD	SEX: Patient sex	Patient	
Jan 1, 2013 to Dec 1, 2017
	
As sex may affect outcomes, this will be included as a covariate in our models
 
M = Male
 
F = Female

HSM	BMI: Body Mass Index [Derived by Innovian]	Patient	
Jan 1, 2010 to Dec 1, 2017
	
Dichotomized according to WHO definition for obesity: BMI>30. This will be combined with ICD code to create a binary Obesity variable (please see below).

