CIHI DAD	CCI: Charleson Comorbidity Index [Derived by HDNS]	Patient	Jan 1, 2010 to Dec 31, 2017 (3 years before and including 30 days after date of surgery)	
To be computed by the HDNS according to protocol (33) using DXCODES (please see above), to be included into model as covariate.
 
Please report both total score, and any of the following individual categories:
 
 Myocardial infarction Congestive heart failure Peripheral vascular disease Cerebrovascular disease Dementia Chronic pulmonary disease Rheumatic disease Mild liver disease Moderate or severe liver disease Diabetes without chronic complication Diabetes with chronic complication Hemiplegia or paraplegia Renal disease Any malignancy, including lymphoma and leukemia, except malignant neoplasm of skin Metastatic solid tumor Peptic Ulcer Disease Excluding Bleeding AIDS/HIV
CIHI DAD	RCRI: Revised Cardiac Risk Index [Derived by HDNS]	Patient	Jan 1, 2010 to Dec 1, 2017 (3 years before and including date of surgery)	As RCRI has been shown to affect outcomes (29), it will be included as a covariate. This is based on DXCODE ICD codes (identified above) of history of ischemic heart disease, congestive heart failure, cerebrovascular disease, diabetes on insulin, chronic kidney disease creatinine >176.8 µmol/L, and a list of Canadian Classification of Health Interventions (CCI codes) of

				
suprainguinal vascular, intraperitoneal, or intrathoracic surgery (30).
 
Detailed protocol will be sent to the HDNS. Please provide both the names of the categories and the total score (i.e. for each patient, positive for any of the categories of cerebrovascular disease, ischemic heart disease, congestive heart failure, chronic kidney disease, diabetes, and diabetes on insulin; as well as the total RCRI score (1 point for each positive category).

CIHI DAD	High risk surgery as per RCRI: Suprainguinal vascular, intraperitoneal, or intrathoracic surgery [Flag - Derived by HDNS]	Patient	3 years before and including date of surgery (i.e. Jan 1, 2010 to Dec 1, 2017)	Binary variable (yes/no) As this may affect outcomes, it will be included as a covariate by itself and as part of the Revised Cardiac Risk Index (RCRI) score calculation.

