Innovian	Preoperative heart rate	Patient	Jan 1, 2013 to Dec 1, 2017	
As this may affect the level of harm from the intraoperative heart rate, it will be used in the calculation of change in heart rate (absolute and %)
 
HSM contains heart rate of elective surgery patients at the anesthetic clinic and prior to entering the operating room, while Innovian contains the initial heart rate of all patients in the operative room. The lowest heart rate from either Innovian or HSM will be used.

CIHI DAD	
Emergency surgery
 
[Derived by HDNS]
 
ENTRYCO D: method of entry
	Patient	Jan 1, 2013 to Dec 1, 2017	ENTRYCOD = E (i.e. emergency department) and/or ADFROM = [any except 085 (QEII) – i.e. transferred from another institution] excluding elective admission (flag) will be used to identify surgeries as emergency surgery. As the emergency nature of surgery has been shown to affect outcomes, it will be included as a covariate.

	ADFROM: Institution from Number			
CIHI DAD	ADTYPE: Admission Type	Patient	Jan 1, 2013 to Dec 1, 2017	This variable will be used internally by HDNS to create a flag for elective admission. This will not be included in the dataset. This will help identify patients who did not have emergency surgery.
Indicator of surgical complexity				
CIHI DAD	CMG: Case Mix Group (“a grouping methodology developed by CIHI that categorizes acute care patients into groups based on similarities of diagnosis, intervention, LOS, and resource requirements.”)	Patient	Jan 1, 2013 to Dec 1, 2017	All CMG will be included into modeling to determine the CMG with the highest postoperative risk.
CIHI DAD	PIMR: Procedural Index for Mortality Risk [Derived by HDNS]	Patient	Jan 1, 2013 to Dec 1, 2017	As the PIMR has been shown to affect outcomes, it will be included as a covariate. HDNS will calculate using DXCODE according to a published protocol (35). Detailed protocol will be sent to the HDNS.
CIHI DAD	Subgroup analysis flag: intermediate to high risk, gender neutral elective surgeries	Patient	Jan 1, 2013 to Dec 1, 2017	To create a list of intermediate to high risk, gender neutral elective surgeries for subgroup analysis. Detailed list of CCI codes will be sent to the HDNS.

	[Derived by HDNS based on PCODE]			

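### Two Appendix 1 rows on procedure risk, the RCRI high-risk-surgery flag and the PIMR, contradict the plan's own rules on look-back and code source

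*Combined protocol and SAP*

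**What the plan says.** **High-risk-surgery flag.** The Appendix 1 row headed High risk surgery as per RCRI defines a yes/no variable for suprainguinal vascular, intraperitoneal or intrathoracic surgery, derived by HDNS. Its time span is "3 years before and including date of surgery (i.e. Jan 1, 2010 to Dec 1, 2017". On its use the row says "it will be included as a covariate by itself and as part of the Revised Cardiac Risk Index (RCRI) score calculation". The RCRI is also a subgroup factor under Sensitivity and subgroup analysis. Table 2 lists the source of the same component as "CCI and Case Mix Group codes of suprainguinal vascular, intraperitoneal, or intrathoracic surgery) using previously published methods" and states no look-back.

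**The general rule.** The PDATE row of Appendix 1 makes one exception, "except for preoperative comorbidity data, where we would need data for 3 years prior to PDATE", and then says "for all other variables we only need data within 30 days after PDATE". It adds that the number of the PDATE matching the Innovian surgery date governs every procedure-related code. The PCODE and PDSERV rows repeat that only the one code for that date is taken.

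**PIMR.** The Appendix 1 row says "HDNS will calculate using DXCODE according to a published protocol (35"). Appendix 1 defines DXCODE as the diagnosis code. Table 2, under indicators of surgical complexity, says "Procedural Index for Mortality Risk (PIMR) (35): according to CCI".

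**The concern.** Both variables are meant to describe how risky the index operation is. Surgical risk plausibly influences both intraoperative hemodynamics and death, so these covariates should refer to the right operation and come from the right field.

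Read literally, the flag row makes a patient with a bowel resection two years earlier and a minor limb operation as the index case high risk for surgery. The same point then enters the RCRI total and can move the patient between RCRI subgroups. The PIMR row directs HDNS to a field that records diagnoses, not operations. HDNS derives both variables, and the plan describes no check of either against the index procedure code.

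**Working it through.** **1. The plan's own figure.** The only sample-size figure is under Power calculation: 0.017 x 24,000 = 408 deaths, and 408 / 10 = 40.8, or about 41 predictors. It reproduces, and this point does not change it. It does show why compact measures of procedure risk are useful: raw procedure codes and Case Mix Groups have many levels to fit within that limit.

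**2. Time spans side by side (Appendix 1).**

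| Row | Time span | Link to the index operation |
|---|---|---|
| High-risk-surgery flag | Jan 1, 2010 to Dec 1, 2017 (three years back) | none stated |
| Flag for intermediate to high risk elective surgery | Jan 1, 2013 to Dec 1, 2017 | based on PCODE |
| CMG | Jan 1, 2013 to Dec 1, 2017 | grouping assigned to the patient's stay |
| PIMR | Jan 1, 2013 to Dec 1, 2017 | none stated; source given as DXCODE |
| PCODE, PDSERV | Jan 1, 2013 to Dec 1, 2017 | the one code for the matched PDATE |

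The high-risk-surgery flag is the only one of these rows with a look-back. The other rows that carry the same three-year span (RCRI, preoperative insulin, preoperative creatinine, Hospital Frailty Risk Score) concern patient history or, for the RCRI, a score built largely from it.

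**3. Which earlier operations could set the flag under the literal reading.** The index case is the first overnight non-cardiac QEII operation from January 1, 2013. An eligible QEII operation from 2013 onward would itself be the index case, so an earlier eligible one can fall in the window only if it predates 2013. For an index case t years after January 1, 2013, the part of the window before 2013 is max(0, 3 - t) years. Assuming uniform accrual, the mean is:

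- 2013: 2.5 years
- 2014: 1.5 years
- 2015: 0.5 years
- 2016 and 2017: 0 years

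For the derivation set as dated in Creating the models (2013 to 2016) the mean is (2.5 + 1.5 + 0.5 + 0) / 4 = 1.125 years. Appendix 1 ends derivation on November 30, 2016, which is 47 months or 3.917 years, giving 4.5 / 3.917 = 1.15 years. For the validation set it is 0 under either split. These are lengths of exposure to possible error, not error rates. Operations outside the eligibility rule (cardiac, short-stay, or at another hospital) could enter the window in any year, so the contrast between sets is not complete.

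**4. Size.** Let q be the share of index operations that truly qualify, and h the share of the remaining patients with a qualifying operation in the previous three years. The false share among flagged patients would be (1 - q)h / [q + (1 - q)h]. The documents give neither q nor h, so no figure follows.

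**5. PIMR.** Three indications point to procedure codes: its place in Table 2 under surgical complexity, the adjacent Table 2 entry for procedure by CCI codes, and the title of reference 35, which describes the influence of procedures on hospital death. One points to diagnosis codes: the Appendix row. That row's sentence matches the one in the Hospital Frailty Risk Score row except for the reference number, and the frailty score is a diagnosis-based measure. A carried-over line is the likely explanation. The abbreviation does not settle it alone, because Appendix 1 uses CCI both for the Charlson index and for the Canadian Classification of Health Interventions.

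**The case against.** The strongest reply is that the plan already contains the right rule. The PDATE row applies the matched date's number to all procedure-related codes, and the RCRI surgical component is built from such codes. The PDATE and PCODE rows request data only from 2013, so the pre-2013 codes that an earlier eligible QEII operation would need are not requested there. The three-year cell may be no more than an extraction window copied from the RCRI row above it. Nothing in the text says an earlier operation should count. Detailed RCRI and PIMR protocols are to be sent to HDNS, and they are not in these documents. If the PIMR cannot be built from diagnoses, HDNS would have to query the instruction before any patient was scored.

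Much of this stands. It means that misclassification cannot be asserted as a fact. It does not remove the conflict: the flag's own row gives only the three-year span, says nothing else about which operation counts, and promises no separate protocol of its own.

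A reader might go further and infer that control for surgical severity fails and that residual confounding of the primary association is established. The documents do not support that. CMG, PCODE and PDSERV also describe the index operation, as do emergency status, duration, laparoscopy and blood loss. Table 2 places the RCRI among competing comorbidity scores, of which the most predictive is to be kept, so the RCRI total may not remain in the final model.

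**Conclusion.** The point holds as two internal contradictions in the specification of procedure risk. The flag row, taken at its word, is a wrong rule: it conflicts with the PDATE, PCODE and PDSERV rows and would let past surgery define the risk of the index operation. The PIMR row names a code source that conflicts with Table 2 and with the nature of the index.

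The consequence is conditional on HDNS applying the rows literally, and its size is not computable from the documents. Two features of the flag error can be stated. It would carry into the RCRI total and the RCRI subgroup. For eligible QEII operations it would touch index cases of 2013-2015 and not those of 2016-2017, so the flag could mean something different in derivation and validation. That second feature rests on the first-operation rule and on pre-2013 procedure data being available to HDNS. For the PIMR, no direction or size of error can be given.

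**What to change.** Change two rows of Appendix 1 and the matching HDNS specification:

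- **High-risk-surgery flag:** derive it only from the PCODE matched to the index PDATE, and set the time span to the index procedure date (Jan 1, 2013 to Dec 1, 2017). State that the surgical component of the RCRI total uses this same flag. If earlier major surgery is of interest, define it as a separate variable.
- **PIMR:** replace the DXCODE source with calculation from the matched PCODE, and write out Canadian Classification of Health Interventions so that it is not read as the Charlson index.

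Before extraction this costs two lines. If HDNS has already delivered the variables, ask which rule was applied. If it was the literal one, the flag, the RCRI total and the PIMR need to be derived again.

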We will exclude patients with no intraoperative anesthetic records. Cardiac surgery patients (identified by procedure anatomy “Heart” or “Cardiac” within Innovian) are excluded since they have a unique set of considerations and complications due to having surgery directly in the heart. To include the full spectrum of non-cardiac surgical patients, no specific surgeries will be excluded except for deceased organ donation (“organ retrieval” in Innovian procedure name, and American Society of Anesthesiologists classification for neurologically-deceased organ donors, ASA=VI).

Preliminary analysis of our intraoperative database estimates approximately 35,000 patients in this cohort. For patients with multiple procedures, the date of the first surgical procedure with an overnight stay will be used to identify the specific surgical admission of interest.

Data Sources

The de-identified dataset will consist of databases from Innovian, Horizon Surgical Manager (HSM), and Health Data Nova Scotia (HDNS). Innovian is the intraoperative anesthesia electronic information management system used at the QEII, containing automated recordings of intraoperative standard monitors, time-stamped anesthesiology entries of medications and interventions, and perioperative laboratory tests. HSM contains vital signs and administrative data at the anesthetic preoperative clinic, in the preoperative area prior to the surgery, and in the recovery room after surgery.

The specific HDNS databases to which access is being requested are the Canadian Institute for Health Information (CIHI) Discharge Abstract Database (DAD) and Vital Statistics. DAD is a repository of clinical and administrative data from each hospitalization, including preoperative diagnoses, surgery performed, postoperative complications, and investigations.

DAD includes the 25 most relevant diagnoses preoperatively and postoperatively. Nova Scotia physician billings data will not provide any additional relevant information and are not necessary for this project. The Vital Statistics database records all deaths within Nova Scotia. Innovian and HSM data will be linked together by health card number and surgical date by the Innovian Data Manager (Innovian-HSM dataset). The health card numbers will be sent to Medavie for encryption. HDNS will link the Innovian-HSM dataset with the HDNS variables by encrypted study IDs and surgery date. National and provincial privacy and data security policies will be strictly followed.

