This study involves a large, recent population dataset with nearly complete follow up for the primary outcome. There has been more than 10 years of experience with intraoperative anesthetic electronic recording system, with a high likelihood of provider proficiency with anesthetic intraoperative electronic documentation. This dataset is unique in North America for its degree of intraoperative details, pairing of clinical and administrative data, and robust data quality. Our use of machine learning could detect new network relationships and strategies that may inform current practice as well as future research.

Limitations

This study involves two academic provincial adult non-obstetric tertiary care centres in one hospital system, which may represent a sicker population. Validation in other centres would

increase generalizability. The retrospective nature of this database study makes it susceptible to random error, bias, and confounding. There may be cluster effects from health providers and hospitals, however the large sample size allows for robust power and minimizes random error. There is a potential for misclassification, measurement, and ascertainment bias. Due to the lack of universal screening for morbidity (e.g. troponin biomarker for myocardial injury and infarction, and Brain-Natriuretic Peptide for preoperative cardiac risk stratification), only mortality will be included as primary outcome. The lack of postoperative hemodynamic data creates non-informative censoring (i.e. unbiased since the data is missing for all patients). Numerous other predictors have been adjusted for through multivariate logistic regression but unknown confounders and confounding by indication may remain. The retrospective data reflects a snapshot of evolving practice, though secular effects may remain limited over the five-year study period. Future prospective validation of the prediction model will increase external validity.

Future directions

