This is a minimal-risk study. De-identified patient data meeting the inclusion and exclusion criteria will be obtained from Innovian and Health Data Nova Scotia. This project satisfies all of the requirements for waiver of consent under the Tri-Council Policy Statement (TCPS 2) and Nova Scotia Personal Health Information Act (please see Request for Waiver of Consent appendix). The population size is estimated to be 35,000, which would be impracticable since this is an incredibly large population to contact for consent. Also, the cohort of interest includes patients aged 45 and older who have undergone surgery, and it is therefore expected that some patients would have died. Obtaining consent for these individuals would not only result in the re-identification of these patients, but also their next-of-kin who would give consent on their behalf. We have submitted a request for waiver of consent to the REB.

Measures will be in place to minimize the risk of breach in privacy and confidentiality (please see below). Due to the large sample size and the collection of common perioperative outcomes, accidental identification of a specific person from de-identified data is unlikely. There is no other adverse event, harm, or risk anticipated.

Health Data Nova Scotia will create a database of linked data using the Provincial Health Card number and date of surgery. The database we receive will be de-identified. PHI collected include the following and will be used in the most de-identified form:

1. Date of surgery (for patients with multiple surgeries, information from only the first surgery will be collected): in order to divide the cohort into derivation, training, and validation groups by date of surgery
2. Age on date of surgery, Sex: potential covariates in the model
3. Procedures (Current Procedural Terminology (CPT) codes: a potential covariate in the model

Measures Taken to Protect Personal Health Information and Study Data

- **Cohort creation:** The linked dataset will be created by HDNS through experienced personnel and established process, and follow Tri-Council guidelines. The dataset we receive for analysis will not contain any direct identifiers such as health card number and date of birth.

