Innovian	Surgical APGAR Score [Derived by Innovian based on variables already requested]	Patient	Jan 1, 2013 to Dec 1, 2017	
  
 	0 points	1 point	2 points	3 points	
   
 Estimated blood loss (mL)	> 1,000	601–1,000	101–600	≤ 100	
 
 Lowest mean arterial pressure (mmHg)	< 40	40–54	55–69	≥ 70	
 
 Lowest heart rate (beats/min)	> 85	76–85	66–75	56–65	
 
 Surgical score (0-10) = sum of all points	
 
 The Surgical APGAR Score is an existing, validated method of risk stratification at the end of surgery, and will be compared to the machine learning models.	
  
		0 points	1 point	2 points	3 points	Estimated blood loss (mL)	> 1,000	601–1,000	101–600	≤ 100	Lowest mean arterial pressure (mmHg)	< 40	40–54	55–69	≥ 70	Lowest heart rate (beats/min)	> 85	76–85	66–75	56–65	Surgical score (0-10) = sum of all points					The Surgical APGAR Score is an existing, validated method of risk stratification at the end of surgery, and will be compared to the machine learning models.					4 points
	0 points	1 point	2 points	3 points																															
Estimated blood loss (mL)	> 1,000	601–1,000	101–600	≤ 100																															
Lowest mean arterial pressure (mmHg)	< 40	40–54	55–69	≥ 70																															
Lowest heart rate (beats/min)	> 85	76–85	66–75	56–65																															
Surgical score (0-10) = sum of all points																																			
The Surgical APGAR Score is an existing, validated method of risk stratification at the end of surgery, and will be compared to the machine learning models.																																			
Mortality																																			
Vital Statistics	Mortality (30-day all cause) [Derived by HDNS based on DOD from Vital Statistics]	Patient	Jan 1, 2013 to Dec 31, 2017	Binary outcome (yes/no), derived from DOD within 30 days from PDATE. This is needed to compute 30-day all-cause mortality. Primary outcome for the study to be used for modeling.																															

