CIHI DAD	OPDEATH: operative death	Patient	Jan 1, 2013 to Dec 31, 2017	OPDEATH will be described in descriptive statistics. 1 = Died in Operating Room 2 = Did Not Die in Operating Room																															
Vital Statistics	DOD: Date of death	Patient	Jan 1, 2013 to Dec 31, 2017	For internal use by HDNS to compute 30-day all-cause mortality (primary outcome), and the Number of																															

				postoperative day of death (i.e. Date of death minus PDATE).
CIHI DAD	Number of postoperative day of death [Derived by HDNS based on DOD from Vital Statistics]	Patient	Jan 1, 2013 to Dec 31, 2017	Derived discrete (n = 1, 2, 3... 30) variable, of the patients with 30-day mortality = yes. This variable is defined as DOD [if \leq 30 days after PDATE] minus PDATE. Survival statistics will be performed (% vs. postoperative day)
CIHI DAD	In-hospital death [Derived by HDNS based on “DISCHARGE: Discharge disposition”]	Patients	Jan 1, 2013 to Dec 31, 2017	Derived binary variable (yes/no). Of those who died within 30 days after surgery, descriptive statistics will be performed for in-hospital vs. out-of-hospital mortality (yes/no) “Yes” if DISCHARGE = 7 or 8: 7 = Died 8 = Cadaver donor admitted for organ/tissue retrieval Else = “no”
Vital Statistics	UCAUSE: Underlying Cause of Death	Patient who died within 30 days after surgery	Jan 1, 2013 to Dec 31, 2017	For patients who died within 30 days of surgery, we are interested in the cause of death. The UCAUSE will only be used internally by HDNS to create flags for these causes of death as categorized according to ICD codes as follows: acute myocardial infarction (I21 to I22, I24), cardiac arrest (I46.0, 146.1, 146.9), ventricular tachycardia (I47.2), shock (R57, T81.1) excluding septic shock (R57.2), congestive heart failure (I50.0, I50.1, I50.9), pulmonary edema (J81), complete heart block (I44.2), pneumonia (J13 to J18, J69.0, J69.8, J95.4), pulmonary embolism (I26), acute respiratory failure (J95.1, J95.2),

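### The primary outcome takes deaths from linked Vital Statistics records alone, so an in-hospital death that fails to link is counted as a 30-day survivor even though the hospital record shows it

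*Combined protocol and SAP*

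**What the plan says.** Appendix 1 defines 30-day mortality as a yes/no variable, "derived from DOD within 30 days from PDATE", and names its source as "Derived by HDNS based on DOD from Vital Statistics". No unknown category is provided. Data Sources gives the reach of that registry: "The Vital Statistics database records all deaths within Nova Scotia". Appendix 1 lists an encrypted health card number for "HDNS data linkage with Vital Statistics" and the same identifier for the DAD.

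Two DAD fields also record death:
- Discharge disposition (DISCHARGE) feeds an in-hospital death variable, whose use is restricted: "Of those who died within 30 days after surgery, descriptive statistics will be performed for in-hospital vs. out-of-hospital mortality (yes/no").
- For the operating-room death field, "OPDEATH will be described in descriptive statistics". Intraoperative mortality is also a secondary outcome.

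Neither field adds to, or is checked against, the primary outcome. The Missing data section expects little missing outcome data because reporting of deaths is compulsory. Strengths claims "nearly complete follow up for the primary outcome" without a figure.

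**The concern.** Someone who survives 30 days has no death record to link to within that window. In Vital Statistics alone, a failed link therefore looks the same as survival, and the source cannot reveal its own failures. Compulsory registration ensures that a death is recorded. It does not ensure that the record is joined to the right study patient.

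The error runs one way, turning deaths into survivors, in the outcome used to build, select and validate the models for the primary outcome. Days alive and out of hospital would inherit it if built on the same death variable. The dataset could also hold a patient coded as died in the DAD and alive at day 30 on the primary outcome, with no rule to reconcile the two.

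**Working it through.** **1. Can the plan detect a missed link?** Data linkage, Step 2, excludes patients with a length of stay of 1 or less, and Appendix 1 derives length of stay from DAD dates. Every included patient therefore has a DAD record, and the discharge death code can be read for the whole cohort. DAD discharge dates are requested to 31 December 2017, which is 30 days after the last surgery date of 1 December 2017. The cross-check is feasible but not planned. That unlinked deaths become survivors is not written in the plan. It follows from a yes/no variable built on one linked date with no failed-link rule.

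The operating-room code adds little. Length of stay is discharge date minus procedure date plus 1, so a death on the procedure date gives 0 + 1 = 1 and leaves the cohort. The discharge code is the more useful check.

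**2. The plan's own figure (Power calculation).** 24,000 × 0.017 = 408 deaths, and 408 / 10 = 40.8, or about 41 predictors. Both reproduce. The 1.7% is an in-hospital rate. It is a fair base for in-hospital deaths that fail to link, but not for deaths after discharge.

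**3. Effect of missing a share m of deaths.** The documents do not give m; 1% to 15% is an assumption. Recorded deaths = 408 × (1 − m). True over recorded deaths = 1 / (1 − m). The false-survivor share is w = 408m / (24,000 − 408(1 − m)). Taking a true AUC of 0.90 for illustration, with misses unrelated to predictors, the observed AUC = 0.90(1 − w) + 0.5w.

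| m | Deaths recorded | Miscoded | Recorded rate | True / recorded | w | AUC |
|---|---|---|---|---|---|---|
| 1% | 403.9 | 4.1 | 1.683% | 1.010 | 0.017% | 0.8999 |
| 2% | 399.8 | 8.2 | 1.666% | 1.020 | 0.035% | 0.8999 |
| 5% | 387.6 | 20.4 | 1.615% | 1.053 | 0.086% | 0.8997 |
| 10% | 367.2 | 40.8 | 1.530% | 1.111 | 0.173% | 0.8993 |
| 15% | 346.8 | 61.2 | 1.445% | 1.176 | 0.259% | 0.8990 |

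At 10 events per predictor, the supported number falls from 40.8 to between 40.4 and 34.7.

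**4. Effect on an association.** For illustration, take risks of 3.4% and 1.7%. The true odds ratio is (0.034/0.966) / (0.017/0.983) = 2.035. If 10% of deaths are missed in both groups, it is 2.032. If 2% are missed in the lower-risk group and 10%, 20% or 30% in the higher-risk group, it falls to 1.863, 1.650 or 1.439.

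**The case against.** A death registry as sole source is a defensible choice. The DAD and Vital Statistics share one key, and elsewhere the protocol says: "Health Data Nova Scotia will create a database of linked data using the Provincial Health Card number and date of surgery". A patient with no usable card number would probably fail the DAD link too and drop out, rather than be scored as a survivor. Limitations mentions misclassification and ascertainment bias. The working shows almost no loss of discrimination, and the larger odds-ratio shifts need an assumed difference in miss rates.

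Most of this stands, and it limits the size of the problem. It does not remove it. A patient can link to the DAD and still fail to match a death record, for instance through an identifier error on one side. The Limitations wording is generic, and no linkage rate or cross-check is planned. Discrimination is only one target: the plan also assesses calibration and hemodynamic associations. If the miss rate were similar in both periods, internal calibration plots would not show the shortfall, because they compare predictions with the same incomplete outcome.

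A reader might go further and infer that many out-of-province referrals are scored as survivors, and might estimate a count by applying 1.7% to an assumed non-resident share. The documents do not support this. They state no residence criterion, but neither do they mention out-of-province patients or say how other provinces' cards are handled. Transfers are described as coming from another institution, not another province. An in-hospital rate also cannot be multiplied by a share dying after they leave, since those deaths would be additional to it.

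**Conclusion.** The point holds for in-hospital deaths that fail to link. They are coded as survivors although a field already requested would identify them, and compulsory reporting does not answer this. The size is unknown and probably small. Over the assumed 1% to 15% range, true deaths exceed recorded deaths by a factor of 1.01 to 1.18. The main effect is on absolute risk and calibration against true mortality, and discrimination is nearly unchanged. Associations would be materially affected only if misses were concentrated in patients with a given predictor value, which the documents neither show nor exclude.

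Separately, because Vital Statistics covers deaths within the province, a post-discharge death elsewhere is not captured. The hospital code cannot repair that. It supports a stated limitation and a qualified follow-up claim, but no numerical estimate.

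**What to change.** 1. Define 30-day death as yes if EITHER the Vital Statistics date of death is within 30 days of the procedure date, OR any DAD record (index or later admission) has DISCHARGE = 7 with a discharge date within 30 days of the procedure date. OPDEATH = 1 also counts.
2. Report the number of records on which the sources disagree. This turns the completeness claim into a measured figure for in-hospital deaths.
3. State under Limitations that deaths outside Nova Scotia after discharge are not captured, and qualify the completeness claim under Strengths.
4. If Health Data Nova Scotia can supply a residence flag, add a sensitivity analysis restricted to Nova Scotia residents. The primary cohort need not change.

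Items 1 to 3 cost protocol wording and a few lines of derivation code on fields already in the request, run by Health Data Nova Scotia. Item 4 needs one extra flag. No patients are lost from the primary analysis.
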